Patients will be asked to complete the questionnaire in a private setting within the infusion centre. Sites will provide patients with appropriate privacy so there is no influence by the physician (or patient perception thereof) in this process. Patients will place their completed questionnaires in an envelope and give the sealed envelope to a study coordinator or designee. Although participating physicians will be informed of the purpose of the study, they will be counselled not to alter routine practice and patient education so as not to influence the study results. Physicians will be advised that the ultimate goal of the study is to evaluate the use of the PAC.

Pretesting of the Patient Questionnaire

To evaluate the patient questionnaires before fielding the study, cognitive pretesting with physicians and patients will be conducted in each country and in each local language. Cognitive pre-test interviewing is a well-established qualitative research methodology

used to identify problems with survey questions and response options (Groves, 2009). Specifically, trained interviewers will ask pre-test participants to complete the questionnaire while thinking aloud or describing their thought processes as they answer the questionnaire items. Pre-test interviewers will use an interview guide that includes probe questions designed to help interviewers understand how each participant interpreted and chose his or her answers for each item in the draft questionnaires. The pre-test interviews will be designed to help identify problems with survey questions, wording, response choices, etc., and ensure that respondents understand the questions. The pre-test interview data will be used to optimise the language used in the questionnaire prior to implementing the patient surveys.

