8.7 DATA MANAGEMENT

A data management plan will be developed to guide the handling of data, including the transfer of electronic files. The data management plan will include, if necessary, country-specific modifications due to local regulations or requirements. The eCRF will be used for both medical record data abstraction and questionnaire completion by patients. The forms will be sent to a data processing centre. Once the forms are received, they will be single-entered into the database. The CRO will follow standard procedures for ensuring accurate data entry, including performing an audit (i.e., a comparison of data on paper to data in the database) of a subset of data entered. Edit and logic checks will be conducted and queries resolved to ensure high-quality data. However, for the patient questionnaire, due to the self-reported nature of the data, some such resolutions may not be possible.

Data managers will conduct UAT of the data entry system and will sign the UAT report before the paper forms are used in the field. Site staff will be trained on data collection forms before the study is fielded. Specialised data managers will approve the data management plan, all annotated data collection forms, data entry system data dictionaries, the data cleaning specifications document, and the testing of summary reports before authorising the data systems to go "live." Data managers will ensure that the paper data systems are tested and valid and will require that testing documentation, database documentation, and change control documentation be created and maintained.

Once the systems are in the field, data management activities will include programming edit checks in preparation for statistical analysis and merging of datasets if required.

Any paper data files collected in the EU will be maintained within the EU. Only deidentified data with case identification numbers will be transferred to the US for data analysis and generation of the final report. Data analysis and storage of de-identified data sets will be in the US. Routine procedures will include checking electronic files, maintaining security and data confidentiality, following analysis plans, and performing quality control (QC) checks of all programs. Each database custodian will maintain any patient-identifying information securely on site according to internal Standard Operating Procedures (SOPs).

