8.7.2 Electronic Case Report Forms

Medical record data will be recorded via eCRF. Patient questionnaires will be self-report, paper-based forms, and data from these forms will be abstracted into eCRF. The source documents will be transcribed by the site on the eCRF. In no case is the eCRF to be considered as source data for this study.

Accurate and reliable data collection will be assured by verification and cross check of the eCRFs against the physician's records and patient questionnaires by the study monitor (source data verification [SDV]). A comprehensive validation check program utilizing back-end checks in the clinical database will verify the data, discrepancies and queries will be generated accordingly and data clarification from the sites will be requested. Queries will be transferred (e.g., via fax or electronic mail) to the site for resolution by the physician.

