10.1 ADVERSE EVENTS SOLICITED VIA THE PATIENT QUESTIONNAIRE (MABTHERA)

The patient questionnaire component of the study is classified as primary data collection. Therefore, individual adverse event information solicited for MabThera via the Patient Questionnaire must be reported to Roche as the Marketing Authorisation Holder.

The Investigational Site Staff must review these Patient Questionnaires and should complete an Adverse Event Reporting Form if there are any adverse events captured. This should then be reported to Roche within the following timelines:

- Serious Adverse Events (SAEs) 24 hours of awareness
- Non-Serious Adverse Events 30 calendar days of awareness

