The questionnaire should take approximately 10 to 15 minutes to complete. Your responses will be kept confidential and will not be shared with your doctor or other health care professionals.

Please answer the following questions to confirm that you are eligible for this study.

S1.	Are you 18 years of age or older?
	□ Yes
	□ No (If no, please speak with your nurse or doctor to confirm your eligibility.)

Questionnaire

The purpose of the study is to learn more about patients' understanding of the important safety information related to MabThera (rituximab). As we are trying to find out your current understanding, please do not look at the MabThera patient alert card or other materials while answering the following questions. The information gathered from this study will help to improve communication about the safe use of MabThera (rituximab).

Note: For review purposes, an asterisk (*) indicates correct responses.

Q1.	Approximately when was your first infusion of MabThera (rituximab)? (Select the one answer that best applies to you.) ☐ This is my first infusion ☐ Less than 3 months ago ☐ Between 3 months and 9 months ago ☐ More than 9 months ago ☐ I don't know
Q2.	During the past 12 months, approximately how many times have you received MabThera (rituximab), which is always given by an IV (intravenous) infusion? 1 time 2 times 3 times 4 times I don't know
Q3.	Where do you get most of your information about MabThera (rituximab)? (Select the one most correct answer.) From my doctor who prescribed MabThera (rituximab) From another doctor at the infusion centre From the nurse at the infusion centre From my chemists/pharmacy¹ From a friend or family member (spouse, adult child) From my professional caregiver From the Internet Other, please specify:

¹ Use "chemists" for UK and "pharmacy" for other countries.

Risk Assessment

The following questions ask about the risks and side effects that patients could potentially experience when taking MabThera (rituximab). Please note these questions are just to learn more about your knowledge of these risks and not about your specific experiences while taking MabThera (rituximab).

Q4.	Has your doctor or other health care professional (e.g., a nurse) ever talked to you about the possible risks of receiving MabThera (rituximab)? ☐ Yes ☐ No ☐ I don't know
Q5.	Which of the following side effects can potentially happen in patients who are receiving MabThera (rituximab)? (Select all that apply.) Hair loss

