Q31.	Which of the following actions did you take when you experienced the most recent infection while undergoing treatment with MabThera (rituximab)? (Select all that apply.)
	☐ When I noticed symptoms, I talked to my doctor
	☐ I referred to my Patient Alert Card
	☐ I told the doctor who treated me for the infection that I was taking MabThera (rituximab)
	☐ I showed the doctor who treated me for the infection the Patient Alert Card for MabThera (rituximab)
	□ None of the above
	☐ I did something not listed here. Please specify:
	☐ I don't know
Q32.	Did you look at the MabThera (rituximab) Patient Alert Card or package leaflet just before or while you were completing this questionnaire? ☐ Yes
	□ No

Demographics

In this last section, please tell us a little information about yourself to help us describe the participants completing this questionnaire.

Q33.	How old are you?
	☐ 18-25 years
	☐ 26-35 years
	☐ 36-45 years
	☐ 46-55 years
	☐ 56-65 years
	☐ 66-75 years
	☐ 76-85 years
	□ > 85 years
Q34.	Are you?
	. □ Male
	☐ Female
Q35.	What is the highest level of education you have completed? (Select one.) ³
	☐ Secondary/high school
	☐ Professional qualifications (for example, nursing, teaching, accountancy)
	☐ Other vocational/work-related qualifications gained at college or in
	employment
	☐ University – Bachelor's degree
	☐ University – Master's degree
	☐ Professional degree (e.g., MD, LLB)
	□ Doctorate degree (e.g., PhD)

Thank you again for taking time to participate in this study! Your answers are very important. If you have any questions about the safety of treatment with MabThera (rituximab), you should talk with your doctor or nurse.

Please place your completed questionnaire in the envelope provided to you by the nurse or doctor and seal the envelope. Also, be sure and let them know that you have finished.

³ Response choices apply to the UK and may need to be adapted for other countries.

5. ENCePP Checklist for Study Protocols

Doc.Ref. EMEA/540136/2009

European Network of Centres for Pharmacoep dem ology and Pharmacovigilance

ENCePP Checklist for Study Protocols (Revision 2, amended)

Adopted by the ENCePP Steering Group on 14/01/2013

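### Patients are told that health care professionals will not see their survey answers, yet site staff must review the questionnaires and the site transcribes them; a conflicting central-entry route adds to the confusion

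*Protocol*

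**What the plan says.** **What the patient is told.** The introduction to the draft questionnaire in Appendix 1 states: "Your responses will be kept confidential and will not be shared with your doctor or other health care professionals". It closes with the instruction: "Please place your completed questionnaire in the envelope provided to you by the nurse or doctor and seal the envelope".

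**How the form is returned.** Section 8.3 (Patient Questionnaire Administration) repeats the arrangement: "Patients will place their completed questionnaires in an envelope and give the sealed envelope to a study coordinator or designee". It gives the reason for privacy: "Sites will provide patients with appropriate privacy so there is no influence by the physician (or patient perception thereof) in this process".

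**Adverse events.** Section 10.1 classes the survey as primary data collection, so that "individual adverse event information solicited for MabThera via the Patient Questionnaire must be reported to Roche as the Marketing Authorisation Holder". The means is review at the site: "The Investigational Site Staff must review these Patient Questionnaires and should complete an Adverse Event Reporting Form if there are any adverse events captured". Serious events are due within 24 hours of awareness and non-serious events within 30 calendar days. Q29 to Q31 ask about infection during treatment, and Q30 offers PML as a tick-box.

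**Data entry.** Section 8.7.2 covers the paper questionnaires and says: "The source documents will be transcribed by the site on the eCRF". It adds source verification by the monitor against the questionnaires and sends queries to the site for the physician to resolve. Section 8.7.1 also makes sites responsible for data entry. Section 8.7 describes another route: "The forms will be sent to a data processing centre", followed by single entry after receipt.

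**The concern.** The survey serves specific aim 2. Several items ask patients to report on the centre that treats them: Q4 on whether risks were discussed, and Q14 to Q20 on whether the card was received, carried, read and explained. The protocol itself treats real or perceived physician influence as something to exclude. That protection depends on the confidentiality sentence being true and on the envelope being handled accordingly.

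The same form is also a safety-collection instrument, and somebody at the site has to read it. The document never says who opens the envelope, when, or whether that person may be part of the treating team. Two things are at stake: whether patients are told the truth about who reads their answers, and whether a solicited infection or PML report is reliably seen at the site.

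**Working it through.** No arithmetic applies, since the point rests on no rate, sample size or error level. The check is to set the provisions side by side and ask which can be followed together.

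| Step | Provision | Source |
|---|---|---|
| Promise | Answers not shared with the doctor or other health care professionals | Appendix 1, questionnaire introduction |
| Return | Form sealed by the patient, handed to a coordinator or designee | 8.3; end of questionnaire |
| Safety review | Site staff must review and complete an adverse event form | 10.1 |
| Entry, route A | Site transcribes, monitor verifies, physician resolves queries | 8.7.1, 8.7.2 |
| Entry, route B | Forms go to a data processing centre for single entry | 8.7 |

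**Promise against safety review.** The reviewers in 10.1 are site staff, with no restriction to non-clinical staff. In an infusion centre these may be nurses or physicians, which is the group the promise names. The promise holds only if every reader happens to be outside that group, and the protocol does not ensure this.

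**Promise against route A.** The site transcribes the form, so at least one member of site staff reads every answer. Queries then go to the physician. That takes questionnaire content to a health care professional by the plan's own procedure, at least for queried items.

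**Sealed return against safety review.** These two are compatible. The text requires the envelope to be sealed at hand-over and does not say that it stays sealed. Sealed hand-over, opening by study staff, review, adverse event form and then entry would satisfy 8.3, 10.1 and 8.7.2 together.

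**Route A against route B.** These are incompatible as places of entry for the same paper form. The version 3.0 entry in the amendment table says that 8.7.2 was amended so that questionnaire data are abstracted into the eCRF, in order to clarify data management. This suggests that site handling is intended and that the sentence in 8.7 is a leftover. It is still current text.

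**Route B against safety review.** Section 8.7 does not say that forms leave the site unopened. If a site read it that way, the review in 10.1 could not take place there and answers to Q29 and Q30 would be unread until central entry.

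**Extent.** The promise and the handling wording apply to every questionnaire: 500 to 700 are projected in 8.1.2, and the final size is set at 500 in 8.5. The review gap under route B concerns only patients who answer yes to Q29; the documents give no figure for how many that would be.

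**The case against.** Four arguments carry weight.

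- **The rules can nearly all be followed.** A reader might infer that the sealed envelope, the site review and the data routes exclude one another. They do not: sealed hand-over and later opening are compatible. What remains is the promise against site access, and route A against route B.
- **Safety reports are not shown to be missed.** A reader might infer that serious events will be reported late against the 24-hour rule. The review duty in 10.1 is explicit and no other section contradicts it. The 24 hours run from awareness, so time before anyone reads the form is not a breach. Q29 asks about infections ever experienced on treatment, so it collects history, and 10.2 separately reminds health care professionals to report reactions not captured in the questionnaire. A gap arises only if 10.1 is ignored and 8.7 is read as shipping unopened envelopes.
- **Bias is not shown.** A reader might infer that reported card receipt and counselling are pushed upwards. Patients answer in private, having read the promise, before anyone opens the form, and later opening cannot change answers already given. An effect needs patients to know or suspect that staff will read the form. No section shows that they would, and neither direction nor size can be derived from the documents.
- **The view of what patients are told is partial.** Written consent comes first, and the consent form is not among the documents; it may disclose the review. The questionnaire is a draft to be modified after cognitive testing. A coordinator or designee need not be a clinician.

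The last argument softens the point without removing it. The draft is appended to the current protocol version, and the sealed envelope also stands in the protocol body. A disclosure in the consent form would not make the questionnaire's own sentence consistent with 10.1. No section keeps clinicians out, and 8.7.2 names the physician for queries.

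**Conclusion.** The point holds as a contradiction in current text with two parts. First, the confidentiality sentence cannot be relied on alongside mandatory site review (10.1), site entry (8.7.1, 8.7.2) and physician query resolution (8.7.2). This affects the wording seen by every survey participant. Second, 8.7 gives a data route that conflicts with 8.7.1 and 8.7.2 and, if read as shipping sealed envelopes, would defeat the site review for patients reporting an infection.

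The documents do not support saying that reports will be missed, that the 24-hour limit will be breached, or that answers are biased in a known direction. The conclusion assumes that the questionnaire would be fielded with this sentence, and that site staff may include members of the care team, which nothing in the protocol rules out. It is worth correcting before fielding, because it concerns what patients are told and who looks for solicited safety information.

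**What to change.** Reconcile 8.3, 8.7, 8.7.1, 8.7.2, 10.1 and the questionnaire introduction before fielding:

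1. Reword the confidentiality sentence so that it says truthfully who at the site will read the form and why, namely adverse event review. Keep the consent form consistent with it.
2. Specify the study role that opens the envelope and carries out the 10.1 review before the form goes anywhere else. Where available, this should be a role not involved in the patient's care.
3. Keep one data-entry route. Delete either the central-entry sentences in 8.7 or the site transcription of questionnaires in 8.7.1 and 8.7.2. In either case, do not send questionnaire queries to the treating physician.

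Moving Q29 to Q31 to a separate unsealed page would not be enough. Q31 includes card-use actions that belong to aim 2, and 10.1 calls for review of the questionnaires, not of one page.

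The cost is minor rewording of the protocol and of one sentence in the questionnaire and its translations. Telling patients that site staff will read the form may cost a little candour. Using a reader outside the care team limits that loss, though some centres may have no such person.

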7. RESEARCH QUESTION AND OBJECTIVES

7.1 OBJECTIVES

- Specific aim 1: To quantify and characterise off-label use through an evaluation of the disease and characteristics of patients treated with MabThera for non-oncology conditions.
- Specific aim 2: To evaluate the extent to which patients receive and read the PAC, knowledge of the PAC content among patients receiving MabThera for nononcology conditions at infusion centres, and whether distribution of the PAC may influence patient actions.

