 - Known and potential risks of infection associated with MabThera including the risk of PML
 - -Symptoms of infection, including PML, and what actions patients should take
 - -Who should not be treated with MabThera
 - -What medication information patients should tell their doctor
 - -Any other counselling received for the infections covered in the PAC
- Patient receipt and reading of the PAC

- -How often has the patient received the PAC?
- –Does the patient currently have a PAC?
- Has the patient received a package leaflet (i.e., PIL)? Does the patient currently have one?
- Patient receipt of additional safety-related information about MabThera
- Patient actions and any changes in behaviour triggered by the PAC (for example, if the patient consulted another physician following the first MabThera treatment or if the patient showed the card to a doctor other than one associated with the MabThera treatment).

Other descriptive information about the patient will be collected to enable stratification of results and facilitate comparison of study participants with the total sample of patients receiving MabThera at participating sites.

Patient Questionnaire Administration

The questionnaire will be completed after the patient arrives at the centre and before the start of the infusion to make sure the questionnaire is completed before any additional counselling regarding the content of the PAC is provided by the site. According to the responses to the feasibility evaluation, all sites considered this to be feasible considering their infusion and counselling practices.

The patient questionnaire will be self-administered (closed-ended questions with predefined answers) on a hard-copy form at the site. The questionnaire will be translated into each local language (English, French, German, Italian, and Spanish) and pretested. Although there are a number of advantages to using an electronic format for questionnaire administration, based on the results of the feasibility evaluation, paper data collection forms are the most efficient approach for this study given the centres' preferences, infrastructure, and the number of patients per centre. Written informed consent will be obtained from each patient prior to completion of this questionnaire.

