Appendix 1 List of Stand-Alone Documents Not Included in the Protocol

- 1. MabThera Patient Alert Card Text for Non-Oncology Indications
- 2. Medical Record Abstraction Form Draft
- 3. Patient Questionnaire Draft
- 4. ENCePP Checklist for Study Protocols

1. MabThera Patient Alert Card Text for Non-Oncology Indications

MabThera Alert Card for patients with non-oncology diseases

Why have I been given this card?

This medicine may make you more likely to get infections. This card tells you:

- What you need to know before having MabThera
- What the signs of an infection are
- What to do if you think you might

be getting an infection.

It also includes your name and doctor's name and phone number on the back.

What should I do with this card?

- Keep this card with you all the time - such as in your wallet or purse.
- Show this card to any doctor,
 nurse or dentist you see not just
 the specialist who prescribes your
 MabThera.

Keep this card with you for 2 years

after your last dose of MabThera.

What else do I need to know?

Rarely MabThera can cause a serious brain infection, called "Progressive Multifocal Leukoencephalopathy" or PML. This can be fatal.

- Signs of PML include:
- Confusion, memory loss or problems

thinking

- Loss of balance or a change in the way you walk or talk
- Decreased strength or weakness on one side of your body
- Blurred vision or loss of vision.

If you get any of these, tell a doctor or nurse straight away. You should also tell them about your MabThera treatment.

Where can I get more information?

See the MabThera package leaflet for more information.

Treatment start date and contact details

Date of most recent infusion:
Date of first infusion:
Patient's Name:
Doctor's Name:

Doctor's contact details:

This is because side effects can develop several months after you have had treatment.

When should I not have MabThera?

Do not have MabThera if you have an active infection or a serious problem with your immune system.

Tell your doctor or nurse if you are taking or have previously taken medicines which may affect your immune system this includes chemo-therapy.

What are the signs of getting an infection?

Look out for the following possible signs of infection:

- Fever or cough all the time
- Weight loss
- Pain without injuring yourself
- Feeling generally unwell or listless.

If you get any of these, tell a doctor or nurse straight away.

You should also tell them about your

MabThera treatment.

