Q12b. Patients should show their patient alert card to any doctor, nurse or dentist involved in their treatment, not just their prescribing specialist physician.	□ Yes*	□ No	☐ I don't know
Q12d. Patients should have a list of all their medicines with them at any visit to a health care professional.	□ Yes*	□ No	☐ I don't know

Q13.	One of the side effects of using MabThera (rituximab) is immune system suppression (a lowering of your body's defenses against infections). How long after stopping MabThera (rituximab) can immune system suppression last? (Select the one most correct answer.)
	☐ A few days
	☐ Several months*
	☐ Two or more years
	□ None of the above
	☐ I don't know

Patient Alert Card Receipt and Review

Now we are going to ask you some questions about the Patient Alert Card that you may have received from your doctor or health care professional. This small, pocket-sized card contains important safety information about MabThera (rituximab).

Q14.	Have you ever received or been given a Patient Alert Card for MabThera (rituximab)?
	☐ Yes → Continue with Question 15
	□ No → Skip to Question 25
	☐ I don't know → Skip to Question 25
	er questions 15-24 only if you have received a Patient Alert Card for hera (rituximab). Otherwise, skip to question 25.
Q15.	How often have you received or been given a Patient Alert Card for MabThera (rituximab)?
	☐ Every time I receive a MabThera infusion
	☐ Some of the times I receive a MabThera infusion
	☐ Only the first time I received a MabThera infusion☐ I don't know
Q16.	Did you have the Patient Alert Card for MabThera (rituximab) with you when you arrived at the centre today? ☐ Yes ☐ No ☐ I'm not sure
Q17.	How much of the time do you keep the Patient Alert Card(s) for MabThera (rituximab) with you? (Select one answer.) All the time Some of the time None of the time I don't know
Q18.	Have you ever read the Patient Alert Card for MabThera (rituximab)? ☐ Yes → Skip to Question 20 ☐ No → Continue with Question 19 ☐ I'm not sure → Continue with Question 19

Q19.	Is there a reason why you have not read the Patient Alert Card for MabThera (rituximab)? (Select all that apply.) Someone else explained it to me I lost the Patient Alert Card I already knew the information I sometimes do not read the materials given to me by my doctor Other

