Q20.	Has someone else, other than the doctor who prescribed MabThera (rituximab) for you, explained the information in the Patient Alert Card for MabThera (rituximab) to you? (Select all that apply.) Yes, a doctor or nurse Yes, a chemist/pharmacist or someone at the chemists/pharmacy² Yes, a friend or family member Yes, a professional caregiver No I don't know
Q21.	What information should patients record on the Patient Alert Card for MabThera (rituximab)? (Select all that apply.) Start date and most recent date of MabThera (rituximab) infusion* Patient's name* Doctor's name and phone number* All of the above* None of the above I don't know
Q22.	How long should patients keep the Patient Alert Card for MabThera (rituximab) after their last dose? (Select the one most correct answer.) 1 week 24 months* 5 years None of the above I don't know

² Use "chemists" for UK and "pharmacy" for other countries.

Q23.	Since starting treatment with MabThera (rituximab), have you seen any doctors for other conditions? ☐ Yes → Continue with Question 24 ☐ No → Skip to Question 25 ☐ I don't know → Skip to Question 25
Q24.	Have you shown the Patient Alert Card for MabThera (rituximab) to doctors treating you for other conditions? ☐ Yes ☐ No ☐ I don't know
Q25.	Have you ever received or been given the package leaflet for MabThera (rituximab)? (Select all that apply.) ☐ Yes → Continue with Question 26 ☐ No → Skip to Question 28 ☐ I don't know → Skip to Question 28
Q26.	Did you have the package leaflet for MabThera (rituximab) with you when you arrived at the centre today? ☐ Yes ☐ No ☐ I don't know
Q27.	How much of the time do you keep the package leaflet(s) for MabThera (rituximab) with you? (Select one answer.) ☐ All the time ☐ Some of the time ☐ None of the time ☐ I don't know
Q28.	Have you ever received or been given other materials that describe the potential risks of receiving MabThera (rituximab)? ☐ Yes ☐ No ☐ I don't know
Q29.	Have you ever experienced an infection while undergoing treatment with MabThera (rituximab)? ☐ Yes → Continue with Question 30 ☐ No → Skip to Question 32 ☐ I don't know → Skip to Question 32

Q30.	Please indicate the most recent infection you experienced while undergoing treatment with MabThera (rituximab)?
	☐ Progressive multifocal leukoencephalopathy (PML)
	☐ Other, please specify:
	☐ I don't know

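### The Q14 skip leaves aim 2 without a receiver versus non-receiver comparison of patient actions, except among patients who report an infection

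*Protocol*

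**What the plan says.** Protocol section 7.1 ends its second aim with the question "whether distribution of the PAC may influence patient actions". Section 8.3 (Patient Survey data) says the questionnaire will record actions prompted by the card and gives two examples: "if the patient consulted another physician following the first MabThera treatment" and "if the patient showed the card to a doctor other than one associated with the MabThera treatment".

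The draft questionnaire in Appendix 1 puts these into practice as Q23, "Since starting treatment with MabThera (rituximab), have you seen any doctors for other conditions", and Q24, whether the card was shown to those doctors. Both lie in a block that patients are to complete, "questions 15-24 only if you have received a Patient Alert Card". No and I don't know at Q14 both route to Q25.

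After the block, Q29 asks everyone about infection during treatment. Only Yes leads to Q31, which lists actions taken at the most recent infection. Two of its options need no card: talking to one's doctor about the symptoms, and telling the treating doctor about MabThera. The second is what the card itself asks of a patient with signs of infection or PML: "You should also tell them about your MabThera treatment".

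Section 8.6 plans to group survey results by, among other things, recency of first treatment and whether the card was read.

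**The concern.** Aim 2 is worded around distribution of the card. Even a purely descriptive answer needs the same action recorded in people with and without the card. Consulting another physician is the protocol's own first example of an action, and Q23 can be answered without a card because it asks only "have you seen any doctors for other conditions". Yet only card-holders are asked it. Q24 cannot serve as a comparator, since a non-receiver has no card to show.

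The knowledge items are placed better. Q5 to Q13 come before Q14 and go to everyone, so knowledge can be tabulated by receipt. Actions, outside infection, cannot. An analysis plan cannot repair this later, because the answers will not have been collected.

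**Working it through.** **Routing.** Following the skip instructions for the four kinds of respondent:

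| Respondent | Q16-17 carrying the card | Q23 saw other doctors | Q24 showed card | Q31 actions at infection |
|---|---|---|---|---|
| Card, infection | asked | asked | if Q23 = Yes | asked |
| Card, no infection | asked | asked | if Q23 = Yes | not asked |
| No card or unsure, infection | not asked | not asked | not asked | asked |
| No card or unsure, no infection | not asked | not asked | not asked | not asked |

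The last row supplies nothing on actions. Only Q31 is put to patients both with and without a card. No item asks an uninfected patient, with or without a card, whether another professional was told about MabThera.

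**The plan's own precision.** Section 8.5 uses p ± 1.96 × √(p(1−p) × DEFF / n), with DEFF = 1 + (8−1) × ICC.
- n = 500, p = 0.75, ICC 0: 1.96 × √(0.1875/500) = 0.038, giving 71.2% to 78.8%, as stated.
- ICC 0.3, DEFF 3.1: 1.96 × √(0.1875 × 3.1/500) = 0.067, giving 68.3% to 81.7%, as stated.

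These are intervals for one proportion in all 500 respondents. They do not describe a comparison by card receipt.

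**How many respondents are affected.** The protocol gives neither a receipt rate nor an infection rate, so both are assumed, and taken as independent.
- Non-receivers skipping Q23: 500 × 0.05 = 25 to 500 × 0.40 = 200.
- Non-receivers reaching Q31, if 10-30% report an infection: 500 × 0.05 × 0.10 = 2.5 to 500 × 0.40 × 0.30 = 60.

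**Precision of a contrast by receipt.** Half-width = 1.96 × √(p(1−p) × DEFF × (1/n₁ + 1/n₀)), with p = 0.5.

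| Assumed receipt | Item asked of all 500, ICC 0 / 0.3 | Q31 only, 20% infected (assumed), ICC 0 |
|---|---|---|
| 70% | 350 v 150: 9.6 / 16.8 points | 70 v 30: 21.4 points |
| 90% | 450 v 50: 14.6 / 25.7 points | 90 v 10: 32.7 points |

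The middle column applies to Q23 put to everyone. A follow-up asked only after Yes at Q23 has fewer respondents and wider intervals. The last column is a floor, because clustering would widen it. Applying DEFF 3.1 there would give 37.7 and 57.5 points, but that is too harsh: 20% of 8 patients is 1.6 per centre.

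**Order of card and infection.** Q29 and Q31 concern infection during treatment. Q15 answers of every infusion, or only the first, place the first card at the first infusion. Order stays open only for those answering some of the times or I don't know.

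**The case against.** The strongest case against is that the protocol does not promise a control group. Sections 8.1.1 and 8.3 speak of actions resulting from, or triggered by, the card, which are card-holder items by nature. Section 8.6 calls the analysis descriptive, and the ENCePP checklist says no measures of effect will be estimated. The parts of FUM 71.1 on using the card, and using it correctly, need no comparator. The card is also meant for every non-oncology patient, so non-receivers may be few, and where distribution differs by centre, counselling may differ too. All of this stands, and it limits what a repaired item can show. It does not explain why an item that anyone can answer is withheld from non-receivers when the aim concerns distribution. Section 6.4 also reports that distribution varied across the feasibility centres, so non-receivers are to be expected.

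A reader might infer more than the documents support:
- *That card-prompted behaviour is measured only at Q23, Q24 and Q31.* Q16 and Q17 record bringing and carrying the card, which the card tells patients to do.
- *That no respondent is asked about telling a doctor.* Q31 asks this of patients with an infection, whether or not they hold a card.
- *That nothing can be compared.* Readers and non-readers among receivers can be compared on Q23 and Q24, although that concerns self-selected reading and not distribution.
- *That infections before card receipt generally count as card-holder actions.* Q15 settles the order for many holders.
- *That 100 or more non-receivers would be gained.* No figure in the protocol supports this.

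**Conclusion.** The point holds in limited form. Outside the infection subset, non-receivers are asked nothing about actions, and no respondent is asked whether another professional was told about MabThera. Receivers and non-receivers can therefore be compared on actions only through Q31. What remains is a one-group description of card-holders, plus readers against non-readers.

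The routing is certain from the questionnaire. The size is not: 25-200 non-receivers, and about 3-60 of them reaching Q31, rest on assumed rates of 5-40% non-receipt and 10-30% infection among 500 surveys. Patients at their first infusion add little either way, since the form is completed before treatment starts. The study can run as drafted, but the change should be made before fielding because the missing answers cannot be recovered.

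**What to change.** - Move Q23 outside the card-only block so that every respondent answers it.
- For those answering Yes, add: *Did you tell them you are being treated with MabThera?* (Yes / No / I don't know).
- Keep Q24 for card-holders.
- Tabulate the new item, and the Q31 options that need no card, by card receipt (Q14) and card reading (Q18).
- Optionally, ask after Q30 whether the card had been received before that infection. This is needed only where Q15 leaves the order open.

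The cost is one changed skip and one or two short items, under a minute per patient. The form is a draft that section 8.3 already sends to cognitive pretesting in each country and expects to modify. The resulting contrast would still be descriptive, non-randomised and possibly confounded by centre, and should be reported as such.
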